#### **6.4 Test of Cure Visit**

The TOC Visit will occur 7 days ( $\pm$ 2 days) after the EOT Visit.

The following procedures will be performed at the TOC Visit:

- Record concomitant medications;
- Perform a limited physical examination, if needed;
- Obtain vital signs, including blood pressure, heart rate, and respiratory rate, and, for ventilated patients, oxygen therapy and respiratory settings including FiO2 and PEEP;
- For patients with HABP, VABP, or VP, perform chest X-ray, MRI, or CT scan;
- Assess clinical signs and symptoms (see [Section 7.5](#));
- Assess clinical outcome. In Part A, clinical outcome will be assessed by the blinded assessor, in addition to the unblinded Investigator (see [Section 7.6](#));

Note: If a patient is a clinical failure at EOT, the patient is automatically considered a failure at the TOC Visit and LFU Visit, and the assessment of clinical response by the Investigator should be listed as “failure at EOT or TOC.”

- Collect blood samples for:
  - Serum chemistry;
  - Serum creatinine;
  - Hematology; and
  - Blood cultures in patients with bacteremia, if applicable;
- Collect urine sample for urinalysis;
- Collect infection site-specific cultures based on diagnosis if clinically indicated (see [Section 7.7](#)); and
- Assess adverse events.

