#### 7.7.1 Respiratory Tract Specimens

For patients with HABP, VABP, or VP, the BPP rapid diagnostic testing at Screening should be conducted using BAL-like specimens (BAL or mini-BAL) or endotracheal aspirate by Protected Endotracheal Catheter specimens, as applicable. See the Laboratory Manual for further details.

For patients with HABP, VABP, or VP that were diagnosed with a positive BPP rapid test of their respiratory specimen at Screening, respiratory specimens for culture and susceptibility testing must be collected again at Screening. All HABP/VABP/VP patients should have additional specimens collected on Day 5, Day 7, EOT, TOC, LFU, and ET Visits from the respective sites as clinically indicated.

Acceptable specimens for culture and susceptibility testing should include at least 1 positive pretreatment sample (ie, sample obtained prior to study drug dosing) obtained by Protected Specimen Brush with BAL or mini-BAL, by non-bronchoscopic BAL, by Protected Endotracheal Catheter suction, or from culture of lung tissue or pleural fluid obtained prior to randomization and treatment. Non-ventilated patients may have specimens obtained via deep expectoration or expectorated/induced sputum or culture of pleural fluid or lung tissue.

All respiratory specimens, even if positive by BPP rapid test for ABC, should be sent to the local microbiology laboratory for Gram stain (expectorated sputum only), culture and pathogen identification, susceptibility testing, and quantification (BAL only).

To be adequate, respiratory samples from expectorated or induced sputum should show <10 squamous epithelial cells and >25 polymorphonuclear neutrophils per 100 × field. Specimens should be cultured regardless of determination of adequacy. However, if the specimen is deemed to be inadequate, another respiratory sample should be collected and cultured.

Gram stains will be conducted per institutional standards, and Gram stain data should be captured in source documents. Colony counts are not expected to be performed on expectorated or induced

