### 7.7.3 Urine Specimens

For patients with cUTI or AP, urine samples will be collected at Screening, Day 5, Day 7, EOT, TOC, LFU, and ET Visits by 1 of the following methods that minimizes the risk of bacterial contamination:

- Clean-catch mid-stream;
- Newly inserted Foley catheter (bag specimens are not permitted);
- Bladder needle aspiration;
- Suprapubic catheter;
- Ureter aspiration; or
- Nephrostomy tube.

Urine cultures will be performed by the local laboratory. The local laboratory will culture each sample for species identification, quantification, and susceptibility testing. Any organism isolated from the urine will be identified by genus and species by the local laboratory. Culture-purified isolates of potential pathogens isolated at baseline and all post-baseline organisms culture-purified

at the local laboratory and not considered to be contaminants as outlined in the Microbiology Laboratory Manual will be sent to the central laboratory for confirmation of identification and susceptibility results. A urine sample taken to support diagnosis or to treat a medical condition within 48 hours prior to the first dose of study drug can be used for baseline microbiologic assessments if the organism(s) cultured was obtained and stored for shipment to the designated central laboratory. Otherwise, a repeat urine sample for baseline microbiologic assessments is required.

Baseline urine cultures must grow 1 or 2 defined bacterial pathogens, each at  $\geq 10^5$  colony-forming units (CFU)/mL. If a patient grows  $\geq 3$  organisms in the urine, the urine culture will be considered contaminated unless  $\geq 1$  of the organisms also grows in a concurrently obtained blood culture.

For post-baseline urine cultures, only those potential pathogens that grow at  $\geq 10^3$  CFU/mL and deemed not to be contaminants as outlined in the Microbiology Laboratory Manual will be culture-purified and sent to the central laboratory for confirmation of identification and susceptibility testing.

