#### 7.7.4 Surgical or Post-Traumatic Wound Specimens

For patients with surgical or post-traumatic wound infections, an adequate clinical specimen for microbiologic evaluation will be collected at Screening, Day 5, Day 7, EOT, TOC, LFU, and ET Visits as long as clinically indicated (ie, as long as there is material to send for culture). Clinical specimens include pus from a wound or abscess and aspirate from the leading edge of cellulitis.

All specimens should be sent to the local laboratory for Gram stain, species identification, and susceptibility testing.

Isolates of potential pathogen(s) culture-purified at the local laboratory will be sent to the central laboratory for confirmation of identification and susceptibility testing results.

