##### Microbiologic eradication:

- For patients with cUTI or AP: the baseline strain of ABC is reduced to  $< 10^3$  CFU/mL on urine culture and negative on repeat blood culture (if positive at baseline); or
- For patients with bacteremia: absence of the baseline strain of ABC on culture.

Microbiologic presumed eradication: no culture was done, and the patient meets clinical criteria for clinical cure.

Microbiologic persistence:

- For patients with cUTI or AP: the demonstration that the urine culture grew  $\geq 10^3$  CFU/mL of the baseline strain of ABC identified at study entry and/or a blood culture demonstrates the same baseline pathogen(s); or
- For patients with bacteremia: presence of the baseline strain of ABC on repeat culture.

Patients who are a persistence at EOT will be considered a persistence at TOC.

Microbiologic presumed persistence: no culture was done, and the patient meets clinical criteria for clinical failure.

Microbiologic indeterminate: if clinically indicated (for cUTI and bacteremia only), no follow-up culture is available, the culture cannot be interpreted for any reason, or the culture is considered contaminated.

Microbiologic recurrence:

- For patients with cUTI or AP: the demonstration that the urine culture grew  $\geq 10^3$  CFU/mL of the baseline strain of ABC identified at study entry at any time after documented eradication at the TOC Visit up to and including the LFU Visit; or
- For patients with bacteremia: a positive blood culture for ABC at any time after documented eradication at the TOC Visit up to and including the LFU Visit.

7.8.2 Microbiologic Outcome for Hospital-Acquired Bacterial Pneumonia, Ventilator-Associated Bacterial Pneumonia, Ventilated Pneumonia, or Surgical or Post-Traumatic Wound Infections

Microbiologic presumed eradication: no culture was done, and the patient meets clinical criteria for clinical cure. For patients with HABP/VABP/VP or surgical or post-traumatic wound infections, where repeat culture samples may not be indicated, presumed eradication based on clinical improvement will be inferred.

Microbiologic presumed persistence: no culture was done, and the patient meets clinical criteria for clinical failure.

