  29. After screening, collect samples only as clinically indicated. To assess the primary indication and follow-up of the presenting indication, all specimens will be sent to the local laboratory for culture and susceptibility testing per institutional standards. Pure cultures of isolated pathogens will be shipped from the local laboratory to the central laboratory for confirmation of species identification, susceptibility testing, and possible molecular characterization.
  30. If the screening sample for culture that is growing ABC is taken per standard of care before the patient or patient's legally authorized representative signs informed consent, that isolate may be used for baseline eligibility and sent to the central laboratory once consent is obtained, as long as the sample was collected within 72 hours prior to randomization. Additional samples for baseline culture should be collected again within 24 hours prior to randomization, at the specified time points and if clinically indicated.
  31. All patients will receive IV treatment for a minimum of 28 doses of ETX2514SUL plus 28 doses of imipenem/cilastatin or 14 doses of colistin plus 28 doses of imipenem/cilastatin (ie, 7 days for those without dose adjustments), as described in the protocol. For patients with normal renal function, study drug infusions will be administered q6h ( $\pm$ 15 minutes) for ETX2514SUL and imipenem/cilastatin and q12h ( $\pm$ 15 minutes) for colistin.
  32. Adverse events should be captured as described in the protocol.

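### In cUTI/AP, Section 7.7.3 requires urine culture at every listed visit but schedule note 29 makes it conditional, so a cured patient left uncultured can score as presumed eradication in Part B

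*Protocol*

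**What the plan says.** Two rules cover follow-up urine culture in cUTI and AP.

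- **Unconditional.** Protocol Section 7.7.3: "For patients with cUTI or AP, urine samples will be collected at Screening, Day 5, Day 7, EOT, TOC, LFU, and ET Visits". The same section adds: "Urine cultures will be performed by the local laboratory". It sets no test of clinical indication.
- **Conditional.** Note 29 to the row for infection-site cultures in Protocol Appendix A, repeated in SAP Table 1: "After screening, collect samples only as clinically indicated". The row covers all infection sites. The TOC list in Section 6.4 agrees: "Collect infection site-specific cultures based on diagnosis if clinically indicated". Sections 6.3.5, 6.3.7, 6.5 and 6.6 carry the same condition.

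The neighboring specimen sections state the condition themselves. Section 7.7.1 asks for follow-up respiratory specimens "from the respective sites as clinically indicated", and Section 7.7.4 limits wound specimens in a similar way.

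For scoring, Section 7.8.1 (and SAP Section 5.5.2.1) reads: "Microbiologic presumed eradication: no culture was done, and the patient meets clinical criteria for clinical cure". Eradication and presumed eradication both count as favorable. Documented eradication in cUTI/AP needs the baseline strain to fall below 10^3 CFU/mL in urine.

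**The concern.** The urine section lacks a qualifier that the respiratory and wound sections both carry, so it reads as a different rule rather than a loose restatement of note 29. Two sites could each follow a current passage and return different endpoint data.

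Where the culture is skipped and the patient is judged cured, the clinical outcome supplies the microbiologic result. In Part B that outcome comes from the unblinded Investigator alone (Section 7.6), so culture is the only independent check. A patient without symptoms whose urine still grows the organism at or above the threshold would be recorded as a success.

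Microbiologic favorable assessment is a listed secondary endpoint for Part B (Protocol Section 7.2, SAP Section 5.2). Section 1.3 presents Part B as supporting evidence for Part A.

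**Working it through.** The plan states no figure on this point, so there is none to reproduce. The check follows one patient through the rules and then sizes the effect.

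**1. A cured cUTI or AP patient with no symptoms at TOC**

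| Step | If the site follows Section 7.7.3 | If the site follows note 29 |
|---|---|---|
| Urine culture at TOC | Taken | May be omitted as not indicated |
| Urine below 10^3 CFU/mL | Eradication, favorable | Presumed eradication, favorable |
| Urine at or above 10^3 CFU/mL | Persistence, not favorable | Presumed eradication, favorable |

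Among cured patients the two routes differ only in the last row, and there only toward success.

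**2. Would another rule catch it?**

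- *ME Population* (Protocol Section 9.1, SAP Section 8.6): a TOC culture is needed only when collection is clinically indicated, so the uncultured patient can stay in.
- *Missing counted as non-responder* (SAP Section 9.3.2): presumed eradication is an assigned category, not a missing value, so this rule does not apply.
- *Indeterminate* (Section 7.8.1, SAP Section 5.5.2.1): this covers an unavailable culture only if one was clinically indicated, and it names cUTI and bacteremia but not AP. A cured cUTI patient whose indicated culture was not done fits both this category and presumed eradication, and no precedence is stated. AP has no such overlap.

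**3. Size among cUTI/AP patients**

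Let c be the clinical cure rate, u the share of cured patients with no culture, and q the share of those who truly persist. The documents give none of them, so the ranges are assumptions: c = 50–90%, u = 10–50%, q = 10–30%.

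False successes = c × u × q

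- Low: 0.50 × 0.10 × 0.10 = 0.005, or 0.5 points
- High: 0.90 × 0.50 × 0.30 = 0.135, or 13.5 points

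**4. Size in a pooled Part B summary**

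Part B also takes pneumonia, bacteremia and wound infections (Section 4.1.3). If cUTI/AP patients make up 10–30% of the summary (assumed), the figures scale to 0.10 × 0.5 = 0.05 points and 0.30 × 13.5 = 4.05 points.

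**5. Effect of the category alone**

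Moving uncultured cured patients from presumed eradication to a non-favorable category shifts the rate by c × u: 0.50 × 0.10 = 5 points to 0.90 × 0.50 = 45 points. This measures sensitivity to classification. It is not an estimate of error, because many of those patients may truly have cleared the organism.

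**The case against.** The case for leaving the plan alone has several parts.

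- *Section 7.7.3 can be read as the specific rule.* Appendix A marks site cultures at all the listed visits, the visit lists refer the reader to Section 7.7, and clinical indication is not defined for urine. This stands as a plausible reading. It does not remove the conflict, because note 29 uses the word only and makes no exception for urine.
- *Indeterminate already covers a missing culture.* It does so in part, for cUTI. If the Section 7.7.3 schedule itself makes a culture indicated, the overlap widens, but the order of precedence is still missing and AP is still outside the clause.
- *Note 29 does not award the success.* Correct. The credit comes from the presumed-eradication definition in Section 7.8.1, and note 29 only permits the culture to be absent. A fix that stops at note 29 would be incomplete.
- *The categories will be tabulated anyway.* SAP Section 9.3.2 plans counts for each response category, split by overall, monomicrobial and polymicrobial infection. It specifies no split by infection site, although efficacy by primary infection site is a secondary objective.
- *There is a mirror rule.* An uncultured clinical failure is scored presumed persistence, which can lower the favorable rate. The upward direction therefore holds among cured patients, not necessarily for the net rate.

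A reader might infer that microbiologic response in cUTI/AP becomes a copy of clinical cure. At an assumed cure rate of 80%, that would mean 0.80 × 0.10 = 8 to 0.80 × 0.30 = 24 points of overstatement. This needs every cured patient to go uncultured (u = 100%) and a cUTI/AP-only denominator. Nothing in the documents says sites will stop culturing.

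**Conclusion.** The collection rules conflict in the current text, and among cured patients the gap resolves toward success. With the assumed ranges, false successes are about 0.5 to 13.5 points among cUTI/AP patients and about 0.05 to 4.05 points in a pooled summary. These figures illustrate scale and do not predict a result.

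The reach is narrow. Patients with cUTI/AP as the qualifying infection enter only Part B, which has no comparator and is summarized descriptively. The SAP analyzes microbiologic response at EOT, TOC and LFU. Protocol Section 7.2 also lists Day 5 and Day 7, but the SAP carries no such analysis. A reader might infer that the pivotal result is at risk. It is not: the Part A mortality comparison, its margin and its power do not depend on these cultures.

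**What to change.** 1. In note 29 (Protocol Appendix A and SAP Table 1) and in Sections 6.3.5, 6.3.7, 6.4, 6.5 and 6.6, limit the clinical-indication condition to the specimen types whose own sections carry it. Urine culture in cUTI/AP would then follow Section 7.7.3, at least at EOT, TOC and LFU where the SAP uses it.
2. In Protocol Section 7.8.1 and SAP Section 5.5.2.1, state that a cUTI or AP patient with no culture at a visit where Section 7.7.3 requires one is indeterminate, not presumed eradication. Name AP in that clause.
3. Confirm that the response-category table planned in SAP Section 9.3.2 shows documented and presumed eradication separately for cUTI/AP.

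The cost is wording in two documents. Section 7.7.3 already requires the cultures, so no procedure is added. The reported favorable rate may be lower. If cultures have already been missed, the second change lowers the rate by c × u, including for patients who had truly cleared the organism. The separate display lets the reader see how much of the rate rests on presumption, and it remains useful if the wording changes come too late for enrolled patients.

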## APPENDIX B: CENTRAL CLINICAL LABORATORY ANALYTES

### Standard Safety Chemistry Panel

Alanine aminotransferase	Albumin
Alkaline phosphatase	Amylase
Aspartate aminotransferase	Bicarbonate
Blood urea/Blood urea nitrogen	Calcium
Chloride	Creatine kinase
Creatinine	Estimated glomerular filtration rate
Gamma-glutamyl transferase	Glucose
Inorganic phosphorus	Lactate dehydrogenase
Lipase	Potassium
Sodium	Total bilirubin
Total protein	Uric acid

### Hematology

Basophils	Eosinophils
Hematocrit	Hemoglobin
Lymphocytes	Mean corpuscular hemoglobin
Mean corpuscular hemoglobin concentration	Mean corpuscular volume
Monocytes	Neutrophils
Platelet count	Red blood cell count
White blood cell count and differential [1]	

1. Manual microscopic review is performed only if white blood cell count and/or differential values are out of reference range.

### Urinalysis

Bilirubin	Blood
Catalase	Glucose
Ketones	Leukocyte esterase
Microscopic evaluation [1]	Nitrite
pH	Protein
Specific gravity	Urobilinogen

1. Microscopic evaluation is performed only as needed based on positive dipstick test results.

A highly sensitive urine or serum (beta human chorionic gonadotropin) pregnancy test will be performed for female patients of childbearing potential only.

### Screening Only

All Screening laboratories will be performed at the local laboratory and may have been collected as standard of care within 48 hours prior to randomization, with the exception of serum creatinine determination, which must be obtained at the local laboratory within 24 hours before the first dose of study drug. All other samples are to be sent to the central laboratory. The Day 5 safety chemistry panel will be performed at the local laboratory and sent to the central laboratory.

## LIST OF ABBREVIATIONS AND DEFINITIONS OF TERMS

Abbreviation	Definition
ABC	Acinetobacter baumannii-calcoaceticus complex
AE	Adverse event
ALP	Alkaline phosphatase
ALT	Alanine aminotransferase
AP	Acute pyelonephritis
APACHE	Acute Physiology and Chronic Health Evaluation
AST	Aspartate aminotransferase
ATC	Anatomical therapeutic class
BMI	Body Mass Index
BPP	Biofire FilmArray Pneumonia Panel
CE	Clinical Evaluable
CFU	Colony-forming units
CI	Confidence interval
COVID-19	Coronavirus Disease 2019
CRA	Clinical research associate
CRABC	Carbapenem-resistant Acinetobacter baumannii-calcoaceticus complex
CSR	Clinical Study Report
CT	Computed tomography
cUTI	Complicated urinary tract infection
DSMB	Data Safety Monitoring Board
ECG	Electrocardiogram
eCRF	Electronic case report form
EOT	End of Treatment
ESKD	End-stage kidney disease
ET	Early Termination
ETX2514SUL	Sulbactam-ETX2514
FiO2	Fraction of inspired oxygen
GFR	Glomerular filtration rate
HABP	Hospital-acquired bacterial pneumonia
ICF	Informed consent form
ICU	Intensive-care units
IRT	Interactive Response Technology
ITT	Intent-to-Treat
IV	Intravenous(ly)
LFT	Liver function test
LFU	Late Follow-up
LLN	Lower limit of normal

Abbreviation	Definition
ME	Microbiologic Evaluable
MedDRA	Medical Dictionary for Regulatory Activities
MIC	Minimum inhibitory concentration
MITT	Modified Intent-to-Treat
m-MITT	Microbiologically Modified Intent-to-Treat
MRI	Magnetic resonance imaging
PCS	Potentially clinically significant
PEEP	Positive end-expiratory pressure
PK	Pharmacokinetic(s)
q6h	Every 6 hours
q12h	Every 12 hours
qSOFA	Quick Sequential Organ Failure Assessment
QTcF	QT interval corrected using Fridericia's formula
RIFLE	Risk–Injury–Failure–Loss–End-stage renal disease
SAE	Serious adverse event
SAP	Statistical Analysis Plan
SOC	System organ class
SOFA	Sequential Organ Failure Assessment
TEAE	Treatment-emergent adverse event
TESAE	Treatment-emergent serious adverse event
TOC	Test of Cure
ULN	Upper limit of normal
VABP	Ventilator-associated bacterial pneumonia
VP	Ventilated pneumonia
WHO	World Health Organization

## 1. INTRODUCTION

This Statistical Analysis Plan (SAP) is created based on Protocol CS2514-2017-0004 (version 4.0, 17 December 2020) and describes in detail the statistical methodology and the statistical analyses to be conducted for the above-mentioned protocol. Any deviations from the SAP after database lock will be documented in the final Clinical Study Report (CSR).

## 2. STUDY OBJECTIVES

This is a 2-part study, with Part A being the randomized, controlled portion of the study in patients with *Acinetobacter baumannii-calcoaceticus* Complex (ABC) hospital-acquired bacterial pneumonia (HABP), ventilator-associated bacterial pneumonia (VABP), ventilated pneumonia (VP), or bacteremia. Part B is the single-group portion of the study and includes ABC infections that are resistant to or have failed colistin treatment or polymyxin B treatment, as detailed in the inclusion criteria.

### 2.1. Primary Objectives

The primary objectives of this study are the following:

- To compare the efficacy of Sulbactam-ETX2514 (ETX2514SUL) plus imipenem/cilastatin to colistin plus imipenem/cilastatin in patients with carbapenem-resistant *Acinetobacter baumannii-calcoaceticus* complex (CRABC) infections in Part A; and
- To compare the incidence of nephrotoxicity, as measured by the Risk-Injury-Failure-Loss-End-stage renal disease (RIFLE) criteria, of ETX2514SUL to colistin in patients with ABC infections in Part A.

### 2.2. Secondary Objectives

The secondary objectives of this study are the following:

- To compare the efficacy of ETX2514SUL plus imipenem/cilastatin to colistin plus imipenem/cilastatin in all randomized patients in Part A;
- To evaluate the efficacy of ETX2514SUL plus imipenem/cilastatin in patients with colistin- or polymyxin B-resistant ABC infections in Part B;
- To estimate the efficacy of ETX2514SUL plus imipenem/cilastatin for each primary infection site;
- To evaluate and compare the safety of ETX2514SUL and colistin;
- To describe the overall safety profile of ETX2514SUL; and
- To determine the systemic exposure of ETX2514 and sulbactam in a small cohort of severely ill patients administered ETX2514SUL in Part A.

